5.4 Withdrawal from trial and discontinuation of treatment

In accordance with legal requirements and International Council for Harmonisation (ICH) – Good Clinical Practice (GCP) guidelines, every subject has the right to refuse further participation in this trial (withdrawal from trial) or refuse further treatment (discontinuation of treatment) at any time and without providing reasons. A subject's refusal should be effectuated immediately upon his/her request.

In addition, a subject may be withdrawn from the trial or be discontinued from treatment at any time at the discretion of the investigator.

Reasons for withdrawal from trial or discontinuation of treatment include (but are not necessarily limited to) progressive disease, AE, pregnancy, death, protocol violation, and lost to follow-up. If the IMP application is discontinued regardless of the reason for discontinuation, the subject should be encouraged to continue in the trial.

The reasons for trial withdrawal or treatment discontinuation are to be fully documented on the electronic case report form (eCRF) and an EoT visit should be completed as soon as possible to the extent possible. Subjects who withdraw from trial before randomization will be considered screen failures. In case of treatment discontinuation, the subject should be encouraged to attend remaining trial visits in line with the schedule of assessments (SoA). If a subject is withdrawn from the trial due to an AE or treatment is discontinued due to an AE, the AE must be followed up as outlined in Section 7.12.2.

If subjects are diagnosed with or have symptoms suggestive of COVID-19 they may not be allowed to attend trial visits until local regulations allow it. Subjects who are diagnosed with COVID-19 after randomization may subsequently be asked to complete trial visits (to the extent possible) via phone until applicable negative test results can be provided (if necessary, additional trial supplies may be shipped to the subject) or be withdrawn from the trial at the discretion of the investigator.

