7.0 VISIT SCHEDULE AND ASSESSMENTS

7.1 Visit schedule

The schedule of assessments (SoA) is provided in Table 3.

The informed consent process must be completed before any other assessment or procedure. The following order of assessments must always be adhered to:

- Patient Reported Outcomes should be assessed before all other clinical assessments or procedures.
- Skin tape stripping and skin biopsies of CKD-aP target areas must be taken after imaging and CTA of CKD-aP target areas.

On-site visit days should preferably be on the same weekday throughout the trial for subjects on dialysis. On-site visits should be aligned with dialysis visits to the extent possible to avoid unnecessary travelling for subjects on dialysis.

Table 3:Visit Schedule

Trial Period	Screening Period	Treatment Period				FU period ¹				
Visit Number ²	1 (Screening)	2 (Baseline)	3	4	5	6	7	8	9 (EoT) ³	10 (FU)
Trial Week		0	1	2	4	6	8	10	12	14
Days from Baseline (Visit 2)	-28 to -1	0	7	14	28	42	56	70	84	
Visit Window	NA	NA	±1	±2	±4	±2	±4	±2	±4	±2
In-clinic or Phone Visits ⁴	In-Clinic	In-Clinic	In- Clinic	Phone	In- Clinic	Phone	In- Clinic	Phone	In- Clinic	In- Clinic
Informed Consent ⁵	Х									
Eligibility Assessment	Х	Х								
Demographics	Х									
CKD History	Х									
Medical History	Х									
CKD-aP Treatment History	Х									
Worst Itch NRS (WI-NRS) – at-home (diary) assessments ⁶		Х	Х		Х		Х		Х	
Worst Itch NRS (WI-NRS) – On-site assessment ^{7, 8}	Х	Х	Х		Х		Х		Х	
Sleeploss due to Itch NRS (SI-NRS) ⁸	Х	Х	Х		Х		Х		Х	
Skin Dryness NRS (SD-NRS) ⁸	Х	Х	Х		Х		Х		Х	
Subject's Global Impression of Change (SGIC) ⁸			Х		Х		Х		Х	
Subject's rating of importance of improvement ⁸			Х		Х		Х		Х	
Subject's indication of CKD-aP treatment area size ^{8,9}		Х	Х		Х		Х		X	
5D-Itch ⁸		Х			Х		Х		Х	
Skindex-10 ⁸		Х			Х		Х		Х	
EQ-5D-5L ⁸		Х			Х		Х		Х	
CKD-aP target area identification		Х								
CGA of Skin Appearance	Х	Х	Х		Х		Х		Х	
CTA of Skin Appearance		X	Х		Х		Х		X	
Physical examination ¹⁰	X	X							Х	(X)
Vital signs ¹¹	X	Х			Х		X		Х	(X)

Trial Period	Screening Period			Tr	eatment	t Period				FU period ¹
Visit Number ²	1 (Screening)	2 (Baseline)	3	4	5	6	7	8	9 (EoT) ³	10 (FU)
Trial Week		0	1	2	4	6	8	10	12	14
Days from Baseline (Visit 2)	-28 to -1	0	7	14	28	42	56	70	84	
Visit Window	NA	NA	±1	±2	±4	±2	±4	±2	±4	±2
Single 12-lead ECG		Х			Х				Х	(X)
Pregnancy Testing ¹²	X	Х			Х				Х	(X)
Laboratory Assessments ¹³	X	Х			Х				Х	(X)
Imaging of CKD-aP ¹⁴		Х			Х				Х	
Randomisation		Х								

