Diary (Handout)	Х	Х	Х		Х		Х			
Biopsy ¹⁵		Х							Х	
Tape stripping ¹⁶		Х							Х	
Prior & concomitant therapies ¹⁷	Х	Х	Х	Х	Х	Х	Х	Х	Х	Х
Adverse events		Х	Х	Х	Х	Х	Х	Х	Х	Х
Investigational medicinal product (IMP) dispensation		Х			Х		Х			
IMP return, compliance and accountability					Х		Х		Х	
IMP application ¹⁸				_	Х					
Diary (Review)		Х	Х		Х		Х		X	

- 1. Follow-up (FU) visit is only applicable if there are ongoing serious adverse events (SAEs) or related adverse events (AEs) at Week 12. (X) indicates assessments to be performed if judged necessary by the investigator.
- 2. An unscheduled visit can be conducted to perform any of the postbaseline assessments or procedures included in the SoA if deemed necessary by the Investigator.
- 3. In the case of trial withdrawal or treatment discontinuation, all assessments of the Week 12 (End of Treatment [EoT]) visit have to be performed. The end of treatment form must be completed when treatment is discontinued and the end of trial form must be completed at end of the trial or in case of trial withdrawal.
- 4. Phone calls: To remind subjects about diary documentation (in particular once-daily WI-NRS assessments that must be performed for 8 days leading up to each on-site visit [i.e., from day -7 to day 0 where day 0 = next on-site visit day]) and to ask for AEs. Phone visits may be replaced by in-clinic visits where relevant, e.g., in subjects going to the dialysis unit for haemodialysis.
- 5. Informed consent must be signed by both subject and investigator before any trial-related procedures are performed.

Clinical Trial Protocol

Protocol No. MC2-25-C1 Vers.3.0 EU/30-Nov-2022

- 6. At-home (diary) assessments must be performed for 8 days leading up to each visit, i.e., from day -7 to day 0 where day 0 = next on-site visit day.
- 7. The WI-NRS must also be reported by the subject at on-site visits
- 8. At all on-site visits, all patient-reported outcome (PRO) assessments should be completed before all other clinical assessments or procedures.
- 9. The trial staff must estimate the % body surface area treated based on the subject's indication of CKD-aP treatment area size on the CKD-aP treatment area diagram.
- 10. Physical exam: A complete physical examination is required at Screening and Week 12 (EoT or Early Termination) visits. An abbreviated physical examination is required at the Baseline visit (and if judged necessary by the investigator) at the FU visit if the FU visit is applicable.

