7.9.1 Worst itch numeric rating score (WI-NRS)

The subject's WI-NRS must be recorded by the subject in a diary once daily (at the same time of the day throughout the trial, i.e., morning, afternoon, or evening for all recordings) on day -7 to day 0 (where day 0 = next on-site visit day) leading up to each visit (8 days in total) at Baseline, Week 1, Week 4, Week 8, and Week 12 or Early Termination using an 11-point numeric rating scale ranging from 0 to 10:

Please score the intensity of the Worst Itch you have experienced in the past 24 hours: 0 (no itch), 1, 2, 3, 4, 5, 6, 7, 8, 9, 10 (very severe/extreme itch).

In addition, the subject's WI-NRS must be evaluated at on-site visits at Screening, Baseline, Week 1, Week 4, Week 8, and Week 12 or Early Termination using the 11-point verbal rating scale above.

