3.1 Primary Efficacy Endpoint

The primary efficacy endpoint is the mean change in weekly mean Worst Itch Numeric Rating Score (WI-NRS) recorded in the subject's diary from Baseline to Week 12 for MC2-25 cream compared to MC2-25 vehicle. Weekly mean WI-NRS is calculated as the average of all and at least 4 non-missing WI-NRS values recorded in the subjects' diaries for the 7 days prior to and including the scheduled in clinic visits (8 days in total expected). If less than 4 observations are recorded in the 8 days expected, the weekly mean WI-NRS will be considered missing.

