5.1 Methodological Considerations

General Conventions:

- SAS[®] software (version 9.4 or higher) will be used for all data analyses and tabulations.
- Data for all investigational centers will be pooled for analysis.
- Summary tables will report data based upon the protocol scheduled time points. For patients who are withdrew early from the study, all efficacy assessments captured at the EoT visit will be assigned to the nearest protocol scheduled time point.

Counts and percentages: Categorical variables will be described by summary tables of frequencies (counts and percentages) per treatment group

Descriptive Statistics:

Descriptive summaries of continuous data will include number of non-missing values, mean, standard deviation (SD), median, minimum, maximum and 1st Quartile (Q1) and 3rd Quartile (Q3). Descriptive summaries of categorical variables will include frequencies and percentages. Missing values will not contribute to the denominator of the percentages.

Statistical tests:

Hypothesis Testing- We assume the null hypothesis is that the MC2-25 cream performs less than or equal to the MC2-25 vehicle while comparing change from baseline in WI-NRS score to Week 12.

We assume for alternate hypothesis that there is significant difference between the treatments.

The hypothesis to be tested to address the objective is:

H0: Change from baseline in mean score of weekly mean of WI-NRS to Week 12 for MC2-25 cream (δ_0) <= Change from baseline in mean score of weekly mean of WI-NRS to Week 12 for MC2-25 vehicle (δ_1)

versus

H1: Change from baseline mean score of weekly mean of WI-NRS to Week 12 for MC2-25 cream (δ_0) > Change from baseline in mean score of weekly mean of WI-NRS to Week 12 for MC2-25 vehicle (δ_1)

The primary analysis will be conducted on Mean change in weekly mean WI-NRS Score recorded in the subject's diary from Baseline to Week 12 for MC2-25 cream compared to MC2-25 vehicle and will be analyzed by a mixed model of repeated measures (MMRM).

Statistical tests will be two-sided with $\alpha = 0.05$. Superiority is concluded if a p-value of statistical hypothesis testing is below the level and the estimate of treatment difference is in favorable direction for MC2-25 cream.

Due to the phase 2 type of the trial, no adjustment due to multiple testing will be used.

No interim analyses are planned. SAS[®] software will be used for all data analyses and tabulations.

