5.2.3 Analysis Windows

As subjects do not always adhere to the protocol visit schedule, the following rules are applied to assign actual visits to analysis visits. Listed below are the visit windows and the target days for each visit. The reference day is Baseline, Study day 1. If a subject has 2 or more actual visits in 1 visit window, the visit closest to the target day will be used as the protocol visit for that visit window. The other additional visit(s) will not be used in the summaries or analyses, but they can be used for determination of clinically important endpoints. If 2 actual visits are equidistant from the target day within a visit window, the later visit is used.

Table 10 represents the analysis windows assigned for efficacy and safety analysis and the corresponding range of treatment days (window) during which data for a particular nominal visit will be collected. The analysis windows will be calculated from the first application of study product. These are analysis windows that contain, but are not same as, the actual visit windows.

For assessments that are not planned on Week 1, the visit window for such assessments will be starting at Week 4.

Study Week/ Period	Study Visit	Target Day	Window
Screening	Visit 1 (V1)	-28 to -1	
Baseline/ Week 0 (on site)	Visit 2 (V2)	1	1
Week 1 (on site)	Visit 3 (V3)	8 (±1)	2-19
Week 4 (on site)	Visit 5 (V5)	29 (±4)	20-43
Week 8 (on site)	Visit 7 (V7)	57 (±4)	44-71
Week 12 (on site/EoT)	Visit 9 (V9)	85 (±4)	72-92
Week 14 (FU)	Visit 10 (V10)	±2 Weeks after EoT	

Table 10Study Period, Visit and Target Day

For the hypothetical strategy, subjects given prohibited therapies will have WI-NRS data set to missing for visits after the start of the prohibited therapies and then missing data will be estimated using MIs. Subjects with an ET visit will be excluded from the PPS analyses. Safety data collected during an ET visit will remain at the Week 12/EoT visit.

Note: As per the CDISC, baseline is defined as Day 1 and not as Day 0. Therefore, there is a difference of one day between study day as defined in protocol and target day (Table 10).

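### Diary WI-NRS is scored only in the 8 days before planned visits, so a subject who withdraws fully at short notice has no weekly mean on 47 to 50 of 83 possible exit days

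*Protocol*

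**What the plan says.** **Collection.** Protocol 7.9.1 asks for one diary score a day "on day -7 to day 0 (where day 0 = next on-site visit day) leading up to each visit (8 days in total"). The rule covers every planned on-site visit from Baseline onward and lists Early Termination as the alternative to Week 12. Table 3 footnote 6 repeats it: "At-home (diary) assessments must be performed for 8 days leading up to each visit". Planned on-site visits are on Days 0, 7, 28, 56 and 84. The phone calls at Weeks 2, 6 and 10 remind subjects of the same 8-day blocks (Table 3 footnote 4).

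**Exit.** Protocol 5.4 says that after withdrawal or discontinuation "an EoT visit should be completed as soon as possible to the extent possible". It also encourages subjects who stop treatment to attend the remaining visits.

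**Scoring.** SAP 3.1: "If less than 4 observations are recorded in the 8 days expected, the weekly mean WI-NRS will be considered missing".

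**Use.** SAP 5.1 says that for early withdrawals "all efficacy assessments captured at the EoT visit will be assigned to the nearest protocol scheduled time point". Where two visits share an analysis window, SAP 5.2.3 keeps the one closest to the target day: "The other additional visit(s) will not be used in the summaries or analyses". Missing weekly means are multiply imputed under missing at random (SAP 5.2.1), with LOCF as a sensitivity analysis.

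**The concern.** The diary rule counts back from a visit whose date must already be known. An unplanned exit has no such date, and the protocol wants the exit visit promptly. By the time the subject decides to leave, most of the days that should have been scored may have passed. A subject leaving on Day 40, for example, has no planned diary day in the preceding week and can contribute at most a score on the day itself. The weekly mean is then missing, and the SAP 5.1 rule has no value of the primary variable to assign.

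Itch shortly before leaving is informative about a withdrawing subject's later course. Missing at random is easier to defend when that level has been observed, and LOCF carries forward whatever was recorded last. If the last weekly mean comes from an earlier visit, both analyses rest on a state that may predate the reason for leaving. For exits inside the Week 12 window, the value lost is at the primary time point itself.

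**Working it through.** **Inputs**
- Visit days 0, 7, 28, 56, 84 (Protocol Table 3).
- Diary block for a visit on Day v: Days v−7 to v (Protocol 7.9.1; Table 3 footnote 6).
- At least 4 of 8 entries for a weekly mean (SAP 3.1).
- Analysis windows at study days 2–19, 20–43, 44–71 and 72–92 (SAP Table 10). Study day is protocol day plus 1, so these are protocol Days 1–18, 19–42, 43–70 and 71–91.
- 108 randomised, 10% dropout (Protocol 8.2).

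Assumptions: planned visits on target, planned diaries complete, no diary entries outside the planned blocks.

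**1. The plan's own figure.** The documents give no figure for unscorable exits. The only related one is the sample size. Control arm: (1 + 1/2) × (1.96 + 0.842)² × 2.46² / 1.5² = 31.7, so 32. Total 96, and 96 / 0.9 = 106.7, so 107 against the planned 108. It reproduces, and nothing below changes it.

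**2. Planned diary days.** −7 to 7, 21–28, 49–56 and 77–84: 15 + 8 + 8 + 8 = 39 days.

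**3. Unscorable exit days.** For an exit on Day t (1 to 83), count the diary days in t−7 to t. The mean is missing if the count is below 4.

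| Gap after visit on | No extra score on exit day | Score added on exit day |
|---|---|---|
| Day 7 | 12–23 (12 days) | 13–23 (11 days) |
| Day 28 | 33–51 (19 days) | 34–51 (18 days) |
| Day 56 | 61–79 (19 days) | 62–79 (18 days) |
| Total | 50/83 = 60.2% | 47/83 = 56.6% |

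Boundary check: on Day 32 the look-back (25–32) holds Days 25–28, four entries. On Day 33 it holds 26–28, three. On Day 51 it holds 49–51, three. On Day 52 it holds 49–52, four. Other denominators (Days 0–84, 1–84, or leaving out planned visit days) give 55.3% to 62.5%.

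**4. Week 12 window.** Exits on protocol Days 71–83 are 13 days. Days 71–79, 9 of the 13, are unscorable in both columns.

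**5. Notice needed.** Entries on the three days before exit plus the exit day make 4. Three days' notice is therefore enough, and a full week is not required.

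**6. Age of the last weekly mean.** At the end of each gap: 23 − 7 = 16, 51 − 28 = 23 and 79 − 56 = 23 days. With the ±4-day windows it can be older: a Week 4 visit on Day 24 gives 51 − 24 = 27. If Week 8 is also booked late, for Day 60, its diary starts on Day 53, Day 55 is still unscorable, and the gap is 55 − 24 = 31.

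**7. Subjects.** 10% of 108 is 10.8, about 11. If all were full withdrawals spread evenly over Days 1–83: 11 × 47/83 = 6.2 and 11 × 50/83 = 6.6. The documents do not give dropout timing. Clustering near planned visits would move this towards 0, and clustering between blocks towards 11.

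**8. Cost of daily scoring.** Days −7 to 84 are 92 days, and 92 − 39 = 53 extra scores per subject.

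**The case against.** Several stronger readings are tempting, and the documents do not support them.

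- **Itch at exit goes unrecorded.** It does not: Protocol 7.9.1 also requires an on-site WI-NRS at Early Termination, on the same 24-hour item. What is lost is the weekly mean. The on-site score is a separate endpoint and is not among the imputation variables that SAP 5.2.1 lists.
- **57% to 60% of dropouts lose their data.** The figure counts days. Subjects who stop treatment but stay keep their planned diary blocks and can supply real Week 12 data, as a treatment-policy analysis needs. The gap concerns full withdrawals.
- **The closest-visit rule is a second large loss.** A planned visit already fills the window on 39 of 83 exit days (8–18, 29–42, 57–70). Without an exit-day score, 27 of those have no mean to displace and are already among the 50. On the other 12 (8–11, 29–32, 57–60), every score in the exit mean is already in the retained planned-visit mean. With an exit-day score, 15 days are scorable and displaced, and each adds one new score. The rule alone therefore costs almost nothing under the present diary.
- **The primary analysis fails, or bias is shown.** Neither follows. Imputation and LOCF are planned, 10% dropout is allowed for, and for exits before Day 71 the lost value belongs to an intermediate visit, with Week 12 imputed in any case.

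It is also fair to say that visit-anchored blocks are a coherent way to limit burden in patients whom the protocol describes as frail, and that the Protocol 5.4 timing is qualified. These arguments limit the size of the point. They do not remove it: without three days' notice, the diary that 7.9.1 requires for Early Termination cannot supply a scorable mean on most exit days.

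**Conclusion.** The point holds for full withdrawals at short notice that fall between diary blocks, and its size is modest. The percentages rest on on-schedule visits and complete planned diaries; missed entries would make them larger. The count of about 6 to 7 subjects also assumes that every dropout is a full withdrawal and that exits are evenly spread. For those affected, imputation and LOCF work from a weekly mean up to 23 days old, somewhat older when the visit windows are used. The day counts do not establish bias or loss of power. This is avoidable loss of primary-endpoint information that can be prevented cheaply, and it is not a flaw that invalidates the analysis.

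**What to change.** 1. **Protocol 7.9.1 and Table 3 footnote 6:** record WI-NRS once daily from the pre-baseline week to Week 12 or EoT, beside the dosing diary that subjects already complete daily (Protocol 6.8; SAP 5.6.1). Weekly means for planned visits stay as defined. Cost: a protocol and diary amendment, and one extra 0–10 score on about 53 more days per subject. The effect of that burden on completion of the required blocks is unknown and should be watched.
2. **SAP 5.2.3, together with item 1:** state that a scorable EoT weekly mean not selected for its window is still used as the last observation for LOCF and as a predictor when later visits are imputed. With daily scores such a mean would hold new information; without them the sentence changes almost nothing.
3. **SAP 5.2.1:** add the on-site WI-NRS taken at Early Termination to the imputation model as an auxiliary variable. It is already collected, so this costs only a line of text, and it is worth doing even if item 1 is declined.

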7.9.2 Sleeploss due to itch numeric rating score (SI-NRS)

The subject's SI-NRS must be evaluated at Screening, Baseline, Week 1, Week 4, Week 8, and Week 12 or Early Termination using an 11-point numeric rating scale ranging from 0 to 10:

Please score how much Sleeploss due to Itch you have experienced in the past 24 hours: 0 (no sleeploss due to itch), 1, 2, 3, 4, 5, 6, 7, 8, 9, 10 (very severe/extreme sleeploss due to itch).

7.9.3 Skin dryness numeric rating score (SD-NRS)

The subject's SD-NRS must be evaluated at Screening, Baseline, Week 1, Week 4, Week 8, and Week 12 or Early Termination using an 11-point numeric rating scale ranging from 0 to 10:

Please score the intensity of the Worst Skin Dryness you have experienced in the past 24 hours in the areas treated with trial medication: 0 (no skin dryness) 1, 2, 3, 4, 5, 6, 7, 8, 9, 10 (very severe/extreme skin dryness).

7.9.4 Subject's global impression of change (SGIC)

SGIC in Worst Itch (WI), Sleeploss due to Itch (SI), and Worst Skin Dryness (SD) must be evaluated at Week 1, Week 4, Week 8, and Week 12 or Early Termination using a 7-item verbal rating scale:

Please choose the response below that best describes the overall change in your (Worst Itch*) since you started taking the trial medication:

- Very much better
- Much better
- A little better
- No change
- A little worse
- Much worse
- Very much worse

*SGIC must be repeated with SI and SD.

7.9.5 Subject's rating of importance of improvement

Subjects reporting an improvement in SGIC ("Very much better," "Much better," or "A little better") must rate the importance of improvements in WI, SI, and SD at Week 1, Week 4, Week 8, and Week 12 or Early Termination using a 2-item Importance Questionnaire:

Question 1:You have reported an improvement in your (Worst Itch*) since you started taking the trial medication. Was the improvement important to you? (Yes/No). If yes, please proceed to question 2.

Question 2: In which way(s) was the improvement in your (Worst Itch*) important to you? (free text)

*Subject's rating of importance of improvements must be repeated with SI and SD.

